#### **II.4.b Assessment of Outcome:**

Samples of carious dentine will be collected with sterile excavator before and after application of intervention/control agent. The dentine samples will be transferred to sterile container containing a 1mL thioglycollate medium used as a carrier, then this sterile container will be kept in an ice box and taken to the microbiology laboratory for processing, within an hour, by another examiner who is blinded to the type of agent applied after partial caries removal. Samples will be vortexed for two minutes, decimally diluted and 0.1 ml will be plated on Mitis Salivarius Bacitracin agar plates, these plates will be incubated anaerobically for 48 hour at 37°C then aerobically for 24 hour at room temperature. The number of colonies will be expressed as colony-forming units (CFU/ml) compared before and after application of the antibacterial agent.

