**I. Materials:**

1. Nano silver fluoride solution (Prepared in Nanotech Co., Egypt) based on silver nanoparticles, chitosan and fluoride. Each tooth will receive two drops of NSF with a micro brush, equivalent to a dose of 10 mg of the solution
2. Chlorhexidine digluconate 2 % solution (Cavity Cleanser, Bisco, USA). Moistens dentin surface after cavity preparation using a micro brush.
3. Rubber dam.
4. Hand spoon excavators.
5. High speed contra angle air-driven hand-piece.
6. Round and round end cylinder carbide and diamond burs.
7. Universal adhesive (Tetric® N-Bond Universal, Ivoclar Vivadent, Schaan, Liechtenstein). The adhesive will be scrubbed into the tooth surface for at least 20 seconds. Followed by dispersing with oil- and moisture-free compressed air until a glossy, immobile film layer results. Light-cure for 10 seconds using a light intensity of  $\geq 500 \text{ mW/cm}^2$ .
8. Bulk-fill resin composite (Tetric® N-Ceram Bulk Fill, Ivoclar Vivadent, Schaan, Liechtenstein) placed in increments of up to 4 mm and cured in 10 seconds ( $\geq 1,000 \text{ mW/cm}^2$ ) or 20 seconds ( $\geq 500 \text{ mW/cm}^2$ ).
9. Medium, fine and extra fine finishing diamond stones and rubber polishing disks.

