**II.4. Trial Description:**

#### **II.4.a Excavation protocol:**

[figure not shown]
The teeth of the patients that meet inclusion criteria will be anesthetized, isolated with a rubber dam. Cavity opened using conventional high-speed rotary instruments. The central cariogenic biomass and the superficial parts of the necrotic dentine will be removed with round burs. Caries lesion will be completely removed in the enamel/dentin junction. The excavation procedure will be terminated as soon as the soft and wet dentine was removed and the remaining tissue was leathery but not hard on exploring. A dentinal sample will then be collected from the base of the cavity using sterile spoon excavator as a baseline for bacteriological assessment. Then, application of either intervention or control agent, another dentinal sample will be collected using a sterile excavator and transferred into sterile tubes and transferred to the laboratory for microbiological analysis.

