## II.6. Sample size calculation:

The aim of this study is to evaluate the antibacterial action Nano Silver Fluoride solution application in comparison to Chlorhexidine solution after partial caries removal in class I carious permanent molar. Based on a previous study by *Mohan et al. 2016*, the expected difference between two interventions is expected to be  $2.1 \pm 2.2 \text{ CFU/mL} \times 10^3$ . Using power 80% and 5% significance level we will need to study 18 in each group to be able to reject the null hypothesis that the population means of the experimental and control groups are equal. This number is to be increased to 22 patients in each group to compensate for possible losses during follow up. The sample size was calculated by PS program.

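### No stated step stops the agent acting between T2 sampling and plating, so the T2 count may include killing in the transport tube

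*Combined protocol and SAP*

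**What the plan says.** Section II.4.a (Excavation protocol) takes the baseline dentine sample (T1) after excavation and goes on: "Then, application of either intervention or control agent, another dentinal sample will be collected using a sterile excavator". It gives no contact time and does not mention rinsing, blotting or drying, either to require or to exclude them.

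Section II.4.b (Assessment of Outcome) sets out the handling in order. On the carrier: "The dentine samples will be transferred to sterile container containing a 1mL thioglycollate medium used as a carrier". On transport: "this sterile container will be kept in an ice box and taken to the microbiology laboratory for processing, within an hour". On processing: "Samples will be vortexed for two minutes, decimally diluted and 0.1 ml will be plated on Mitis Salivarius Bacitracin agar plates". Two incubations and a colony count follow. The broth's only stated function is to carry the sample. No neutraliser, wash of the sample or carry-over control is named anywhere in the protocol.

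Both agents are liquids applied by micro brush (I. Materials). The comparator is "Chlorhexidine digluconate 2 % solution (Cavity Cleanser, Bisco, USA"), with no volume given. For NSF the text reads "Each tooth will receive two drops of NSF with a micro brush, equivalent to a dose of 10 mg of the solution", with no silver concentration.

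**The concern.** A post-application count is meant to show how many bacteria survived the agent in the dentine. That holds only if exposure ends when the sample is taken, or if what happens afterwards is negligible. The written chain does neither. Agent that comes across on the excavated dentine enters the same 1 mL as the bacteria and stays with them until plating.

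Three features make this more than a missing detail:

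- T2 is the only post-treatment measurement, so the trial's conclusion rests on it.
- T1 precedes the agent. A before/after comparison therefore subtracts a count without carry-over from one that may have it.
- The effect follows whichever agent is in the tube. Randomisation balances patients and teeth, and the blinded laboratory examiner and statistician (II.9.b, II.9.d) guard against biased reading. None of these changes what the agent does in the broth.

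A difference between arms, or the lack of one, could then arise partly in transport.

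**Working it through.** **1. The handling chain.** Each written step from application to plating was checked for anything that would end the agent's action.

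| Step | Section | Ends the agent's action? |
|---|---|---|
| Agent applied | II.4.a | No; contact time not given |
| T2 dentine excavated | II.4.a | Nothing stated |
| Into 1 mL thioglycollate | II.4.b | Dilutes; no neutralising role stated |
| Ice box, up to one hour | II.4.b | May slow it; not a neutralising step |
| Vortex, decimal dilution | II.4.b | Dilutes, but only after the time in the tube |
| 0.1 mL plated | II.4.b | Dilutes further |

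**2. Chlorhexidine in the tube.** From the documents: 2%, which is 20 mg/mL = 20,000 µg/mL, and a 1 mL (1,000 µL) carrier. Assumed: the volume v carried over on the dentine.

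Concentration = 20,000 × v / (1,000 + v) µg/mL

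- v = 0.1 µL: 2.0 µg/mL
- v = 1 µL: 20.0 µg/mL
- v = 5 µL: 99.5 µg/mL
- v = 10 µL: 198.0 µg/mL

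The same sum cannot be done for NSF because no silver concentration is given. These are concentrations, not kill fractions. No kill fraction can be derived from the documents.

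**3. The plan's sample size.** II.6 states that "the expected difference between two interventions is expected to be" 2.1 ± 2.2 (× 10³ CFU/mL), with 80% power and 5% significance; II.12 makes tests two-tailed.

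n per group = 2 × [2.2 × (1.960 + 0.842) / 2.1]² = 17.23, rounded up to 18

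This reproduces the stated 18. With the noncentral t distribution, power is 79.4% at 18 per group and 87.1% at 22.

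**4. What an arm difference in tube killing would do.** Let b be the difference between arms in mean T2 count caused by the tube alone (assumed, × 10³ CFU/mL). Because T1 has no carry-over, b passes in full into the difference in T2 means and into the difference in mean change. Two-sided t-test, SD 2.2, 22 per group:

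| b | Significant result when there is no true difference | Power when b opposes a true difference of 2.1 |
|---|---|---|
| 0 | 5% | 87.1% |
| 0.25 | 6.6% | 77.8% |
| 0.5 | 11.4% | 65.4% |
| 1.0 | 31.3% | 36.7% |
| 1.5 | 59.9% | 14.3% |
| 2.1 | 87.1% | 5% |

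At 18 per group the no-difference rates are 6.3%, 10.2%, 26.3%, 51.1% and 79.4% for the five non-zero values of b.

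**5. Equal carry-over.** If the tube killed the same fraction f of survivors in both arms, the absolute T2 difference would be multiplied by (1 − f). With f = 0.25 (assumed), 2.1 becomes 2.1 × 0.75 = 1.575. It would cancel only on a ratio or log scale, and II.12 plans no such scale.

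**The case against.** The case against is substantial, and much of it stands.

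- **Silence is not proof.** A reader might infer that the T2 dentine is still wet with agent and is never rinsed. The text does not say so, and a figure in II.4.a is missing from the copy read. What can be said is that no such step is stated. A rinse would reduce carry-over but would not inactivate agent held in the dentine.
- **Direction.** It is tempting to argue that a thiol broth would quench silver and not chlorhexidine, so that the error favours chlorhexidine. Nothing in the documents supports this, and it carries no weight here.
- **Exposure time.** A reader might set an hour in the tube against a short contact in the tooth and conclude that the tube dominates. The contact time is not stated. On the assumed volumes of 1 to 10 µL, the tube concentration is also about 1,000 to 100 times lower than the 20,000 µg/mL applied (20,000/20 and 20,000/198), and the tube is on ice.
- **Upper case.** The stated NSF dose is 10 mg, about 10 µL at an assumed 1 mg/µL. Carrying 10 µL over would mean the whole dose, so that value is a ceiling for NSF. No chlorhexidine volume is stated.
- **Size.** Every value of b above is assumed. The table shows what an imbalance would do, not how large it is.

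These points limit what can be claimed about size and direction. They do not supply the missing step: ice, the one-hour limit and dilution lessen the action, and nothing stated ends it.

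**Conclusion.** The concern holds in a limited form. As written, the plan has no step that stops the antibacterial action between application and plating, so the T2 count may combine killing in the tooth with killing in the tube. T1 cannot correct it, and with two different agents equal carry-over cannot be assumed.

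The size and direction of any bias are unknown. The 20 to 198 µg/mL range rests on an assumed carry-over of 1 to 10 µL. The error rates rest on assumed arm differences and the plan's SD of 2.2. They show that a modest imbalance would matter: 0.5 × 10³ CFU/mL, about a quarter of the planned difference (0.5/2.1 = 0.24), roughly doubles the false-positive rate. The documents do not support a claim that either agent is favoured, or that tube killing is in fact large.

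The point concerns the validity of the outcome; the 18 and 22 per group are unaffected. It should be settled before recruitment, because samples plated without a neutraliser cannot be repaired afterwards.

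**What to change.** 1. In II.4.b, replace the plain thioglycollate carrier with a single 1 mL carrier containing neutralisers for both agents, used for T1 and T2 in both arms. The microbiology laboratory should choose the formulation, and the check in item 2 should decide whether it is accepted.
2. Before the first patient, run a bench recovery check: a known *S. mutans* suspension in the carrier with and without each agent, held 60 minutes on ice, then plated as in II.4.b. Add a control showing that the neutraliser itself does not reduce recovery. State the acceptance limit beforehand, for example recovery within 0.3 log10 (about twofold).
3. Record the times of application, T2 sampling and plating for each tooth, and tabulate them by arm.

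If a neutralising step is already the laboratory's practice, writing it into II.4.b together with its recovery data would settle the point.

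The cost is a different broth, a few days of bench work and three time fields on the form. There are no extra patients or visits, and the clinical procedure does not change.

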## II.5. Participant timeline:

All clinical procedures will be carried out at the same visit.

## II.6. Sample size calculation:

The aim of this study is to evaluate the antibacterial action Nano Silver Fluoride solution application in comparison to Chlorhexidine solution after partial caries removal in class I carious permanent molar. Based on a previous study by *Mohan et al. 2016*, the expected difference between two interventions is expected to be  $2.1 \pm 2.2 \text{ CFU/mL} \times 10^3$ . Using power 80% and 5% significance level we will need to study 18 in each group to be able to reject the null hypothesis that the population means of the experimental and control groups are equal. This number is to be increased to 22 patients in each group to compensate for possible losses during follow up. The sample size was calculated by PS program.

## II.7. Recruitment:

Patients will be recruited from outpatient clinic of Conservative Dentistry Department in Faculty of Dentistry, Cairo University; after explaining the benefits/risks from the application of the interventions, then eligible patients will be recruited to fulfil the eligibility criteria according to participant timeline.

### **II.8.a. Recruitment Strategy:**

The patients will be subjected to full examination and diagnosis using dental charts. Once the patients that are potentially eligible for this study are identified, they will be contacted by the researcher who will explain the study and ascertains the patient's interest. If interested, more detailed evaluations and preparations are made.

### **II.9. Randomization and assignment of interventions:**

#### **II.9.a. Allocation sequence generation:**

The allocation sequence will be generated using ([www.randomization.com](http://www.randomization.com)).

#### **II.9.b. Allocation concealment mechanism:**

The randomization unit was the tooth, and the randomization procedure will be performed as follows. A number corresponding to each treatment group will be printed on pieces of paper and kept in dark containers. A paper will be selected from the container by a person other than the operator, and the treatment indicated will be performed (intervention/control). Blinding of the operator is not possible, because the color of intervention and control solution is different. The operator is blinded until randomization into groups, to avoid biases with regard to the application of antibacterial agent. Also, the examiner who will carry the microbiological analysis of dentin samples will be blinded to the type of agent

applied during treatment. Finally, the treatment results will be assessed blindly by a statistician.

***II.9.c. Implementation:***

[name] [name] (co-supervisor) will perform the allocation sequence and assign the participants to the intervention/Control treatment group.

***II.9.d. Blinding:***

The side to which interventions or control is assigned to will be recorded and all records of all patients will be kept with the main supervisor. Blinding of the operator is not possible, because the color of intervention and control solution is different. The operator is blinded until randomization into groups, to avoid biases with regard to the application of antibacterial agent. Also, the examiner who will carry the microbiological analysis of dentin samples will be blinded to the type of agent applied during treatment. Finally, the treatment results will be assessed blindly by a statistician.

**II.10. Data collection methods:**

**\*Baseline data collection:**

For every patient medical history, dental history and examination charts will be filled by the operator. The report will be anonymous where patients identified by their serial numbers (the first letter of the first and last name and date of birth) only will be registered. Full detailed personal data of the patient will be written in separate sheet having the patient's serial number for further contact with patient.

\*Outcome data collection:

The results will be converted into a table to facilitate the description of the results. The microbiological analysis will be performed blindly in relation to the type of solution applied after partial caries removal.

## **II.11. Data management:**

The data will be entered and stored on a personal computer. Double data entry will be saved on an external hard disc to prevent loss of data.

## **II.13. Monitoring:**

### **II.13.a. Data monitoring:**

The main supervisor will monitor this study. His role is to monitor any risk of bias could be done from participants, operator or assessors. Also to monitor blinding of the assessors and patient safety, outstanding benefits or harms.

## **II.13.b. Harms:**

The main supervisor should inform participants about the possible harms, if present. Participants are allowed to contact the operator at moment through telephone. In case of accidental pulp exposure during excavation , emergency access cavity and pulp extirpation will be done by the operator and then the patient will be referred to Endodontic Department clinic to complete the root canal treatment.

## **II.13.c. Auditing:**

In the present trial, auditing will be done by the main and co-supervisors to assure quality of the research frequency procedures.

## **II.14. Ethics and dissemination**

### **II.14.a. Research ethics approval:**

Application forms for carrying out the clinical trial, checklist and informed consent of Research Ethics Committee (REC) Faculty of Dentistry, Cairo University will be retrieved and filled, then will be delivered for (REC) committee for approval. This is done to prevent any ethical problems during the study or any harm for any of the participants.

### **II.14.b. Protocol amendments:**

If a new protocol will be used a protocol amendment will be submitted; containing a new copy of the new protocol and brief explanation about the differences between it and the previous protocols. If there is a change in the existing protocol that affects safety of subjects, investigation scope or scientific quality of the trial,

an amendment containing a brief explanation about the change will be submitted. If a new author will be added to accomplish the study, an amendment including the investigator's data and qualifications to conduct the investigation will be submitted to prevent ghost authorship.

#### **II.14.c. Consent:**

The operator ([name]) is responsible for admitting and signing the written consents during the enrolment day.

#### **II.15. Confidentiality:**

Name, personal data and pictures of the participants will not appear on the protocol form and will be maintained secured for 10 years after the trial. This is done for protection of participants' privacy and civil rights.

#### **II.16. Declaration of interests:**

There is no conflict of interest, no funding or material supplying from any parties.

#### **II.17. Access to data:**

Access to final data will be allowed to the operator ,the main and co-supervisors of the study who are not involved in assessment of the outcome.

#### **II.18. Ancillary and post-trial care:**

Patients will be followed up after the application after 3, 6 months.

#### **II.19. Dissemination policy:**

Full protocol will be published online in [www.clinicaltrials.gov](http://www.clinicaltrials.gov) to avoid repetition and to keep the integrity of the research work. Thesis will be discussed in front of judgment committee. The study will be published to report the results of this clinical trial.

